3.1.1. Adverse Events

Any events occurring following start of treatment on Day 1 or increasing in severity will be counted as treatment emergent.

Events that occur during follow-up (ie post-dose non treatment period)) will be counted as treatment emergent and attributed to the previous treatment taken.

3.1.1.1. Hypoglycemia Monitoring and Reporting

Hypoglycemia AEs will be recorded in the Case Report Form (CRF) on a specific page. Details of when these will be recorded are given in the protocol Section 8.2.4.2.

For programming purposes, the hypoglycemic AE categories are based on the following:

- Severe Hypoglycemia: Severe is checked in the severity criteria of the CRF. This assessment will be made by the PI based on the protocol definition.
- Documented Symptomatic Hypoglycemia: If
 - (1) – Did the participant have symptoms of hypoglycemia? Yes
 - and (2) – Was the blood glucose measured? Yes
 - and result \leq 70 mg/dL on the CRF,
 - but hypoglycemia is not classified as severe.
- Asymptomatic Hypoglycemia: If
 - (1) No
 - and (2) Yes
 - and result \leq 70 mg/dL on the CRF,
 - but hypoglycemia is not classified as severe.
- Probable Symptomatic Hypoglycemia: If
 - (1) Yes and
 - (2) No and
 - (2b) – If blood glucose was not measured, did symptoms resolve when treated with carbohydrate or glucagon? Yes on the CRF,
 - but hypoglycemia is not classified as severe.

3.1.2. Safety Laboratory Tests

Safety laboratory tests as described in Section 10.2 Appendix 2 of the protocol will be performed at times defined in the schedule of activities.

Baseline will be the last predose measurement on either Day -1 or Day 1, as applicable.

3.1.3. Vital Signs

Single supine blood pressure and pulse rate measurements will be taken at Screening, Follow-up and at early termination (if applicable). Triplicate supine measurements will be taken at all other times as detailed in the Schedule of Activities given in the protocol.

Baseline will be defined as the time-matched value from the average of the triplicate recordings on Day -1.

The time-matched double difference in supine blood pressures and pulse rate measurements is calculated in the following steps: (1) subtract predose value on Day 1 from all postdose values; (2) subtract the value at 0 hours on Day -1 from all other values on Day -1; (3) take the difference between the adjusted postdose value in (1) and its time-matched value in (2).

3.1.4. Electrocardiograms

A single 12-lead ECG will be obtained on all participants at screening, follow-up and at early termination (if applicable). 12-lead ECGs will be recorded in triplicate at all other times as detailed in the Schedule of Activities given in the protocol.

The average of the triplicate readings collected at each assessment time will be calculated for each ECG parameter.

ECG endpoints include heart rate, QT interval, PR interval and QRS interval. If not supplied QTcF will be derived using Fridericia's heart rate correction formula:
$$QTcF = QT / (RR)^{(1/3)}$$
, where RR = 60/HR (if RR is not provided).

Baseline will be defined as the time-matched value from the average of the triplicate recordings on Day -1.

The time-matched double difference in heart rate, QT, QTcF, PR and QRS measures is calculated in the following steps: (1) subtract predose value on Day 1 from all postdose values; (2) subtract the value at 0 hours on Day -1 from all other values on Day -1; (3) take the difference between the adjusted postdose value in (1) and its time-matched value in (2)

3.2. Secondary Endpoint(s)

[figure not shown]
Blood and urine samples for PK analysis of PF-07081532 will be taken according to the Schedule of Activities given in the protocol.

Plasma and urine PF-07081532 PK parameters following single or multiple dose administration of PF-07081532 will be derived using standard noncompartmental methods, as data permit, for each treatment and day (as appropriate), from the concentration time profiles as follows:

Table 2. PF-07081532 PK Parameters

| Parameter | Analysis Scale | PF-07081532 |
|--------------------|----------------|-------------|
| AUC ₂₄ | ln | D |
| CCI | | |
| C _{max} | ln | D |
| CCI | | |
| T _{max} | R | D |
| t _{1/2} * | R | D |
| CCI | | |
| | | |
| | | |
| | | |
| | | |
| Ae ₂₄ | ln | D |
| Ae ₂₄ % | ln | D |
| CL _r | ln | D |

Key: D=displayed with descriptive statistics, ln=natural-log transformed, R=raw (untransformed), *=if data permits.

CCI

The figure consists of two main sections. The top section is a grid of bars. The first row of the grid contains three black bars of increasing height from left to right. The second row contains four black bars of increasing height from left to right. The third row contains five black bars of increasing height from left to right. The fourth row contains six black bars of increasing height from left to right. The fifth row contains seven black bars of increasing height from left to right. The top-left cell of the grid contains the text 'CCI' in red. The bottom section of the figure contains five long, thick black bars of varying lengths, arranged vertically from top to bottom. The first bar is the shortest, the second is the longest, the third is the second longest, the fourth is the third longest, and the fifth is the fourth longest.

3.4. Baseline Variables

Baseline for all parameters discussed in section 5 and 6 will be defined as the values assessed on Day -1 or Day 1 0H (ie pre-dose).

When three assessments are performed at baseline, the baseline will be the average of the three values CCI

3.5. Safety Endpoints

See section 3.1.

4. ANALYSIS SETS (POPULATIONS FOR ANALYSIS)

Data for all participants will be assessed to determine if participants meet the criteria for inclusion in each analysis population prior to unblinding and releasing the database and classifications will be documented per standard operating procedures.

All analyses will be performed on an “as-treated” basis and will not include data from participants who are randomized but not treated. If a participant takes a treatment that is not consistent with the treatment they are randomized to, for example takes a treatment out of

sequence or takes the same treatment twice, then they will be reported under the treatment that they actually receive for all safety, PK CCI analyses, where applicable.

Participants who experience events that may affect their PK profile (eg vomiting) may be excluded from the PK analysis. At the discretion of the pharmacokineticist a concentration value may also be excluded if the deviation in sampling time is of sufficient concern or if the concentration is anomalous for any other reason.

A full list of protocol deviations (eg medication errors) will be compiled and reviewed to identify major and minor deviations prior to database closure.

| Population | Description |
|--|--|
| Enrolled | All participants who sign the ICD. |
| Randomly assigned to investigational product | All participants randomly assigned to investigational product regardless of whether or not the investigational product was administered. |
| Evaluable | All participants randomly assigned to investigational product and who take at least 1 dose of investigational product. Participants will be analyzed according to the product they actually received. |
| Safety | All participants randomly assigned to investigational product and who take at least 1 dose of investigational product. Participants will be analyzed according to the product they actually received. |
| PF-07081532 PK Concentration Set | The PF-07081532 PK concentration population is defined as all randomized participants who received at least 1 dose of PF-07081532 and in whom at least 1 plasma concentration value is reported. |
| PF-07081532 PK Parameter Set | The PF-07081532 PK parameter population is defined as all randomized participants who received at least 1 dose of PF-07081532 and in whom at least 1 parameter value is reported. |
| | CCI |
| | |

| Population | Description |
|------------|-------------|
| | CCI |

5. GENERAL METHODOLOGY AND CONVENTIONS

5.1. Hypotheses and Decision Rules

Not applicable

5.2. General Methods

5.2.1. Analyses for Binary Endpoints

Not applicable

5.2.2. Analyses for Continuous Endpoints

Continuous endpoints and relevant safety endpoints will be presented using summary statistics: number of observations, arithmetic mean, standard deviation, median, minimum and maximum values.

5.2.3. Analyses for Categorical Endpoints

Categorical endpoints and relevant safety endpoints will be presented using summary statistics: number of observations, counts and percentages.

5.2.4. Longitudinal Analysis using Mixed Model Repeated Measures (MMRM) model

MMRM models will include the change from baseline of the relevant endpoints as specified in [Section 6](#) as the dependent variable and will include treatment, baseline, day, baseline*day interaction and the day*treatment interaction, with day fitted as a repeated effect, and participant as a random effect.

An unstructured covariance matrix will be used to estimate the variances and covariance within participant across time points. If convergence is not obtained or model fit is not adequate then other covariance structures will be investigated as necessary. The Kenward-Roger approximation will be used for estimating degrees of freedom for the model parameters. Missing values will be imputed as part of the MMRM model assumptions.

The Least Squares Means (LSMeans) together with 90% confidence intervals and standard errors will be obtained for each treatment and day. Differences in LSMeans between each treatment and placebo, together with 90% confidence intervals and standard errors, will also be obtained.

Standard SAS output will be provided to support the main statistical summary table for the models.

5.2.5. Bayesian Emax Model

A Bayesian dose-response Emax model will be **CCI** and applied to the change from baseline (CFB) to Day 28 (Part A) and (as sensitivity analysis) Day 42 (Part C) **CCI**. A four-parameter Emax model will include sustained dose for at least 5 days (ie after completing titration phase) as a continuous variable and baseline **CCI** as a covariate. The change from baseline will be assumed to be normally distributed with mean of 'Pred' and standard deviation of 'Sigma' as defined below:

$$CFB = \text{Normal}(Pred, Sigma)$$

Where:

$$Pred = E_0 + \frac{E_{max} \times dose^{Hill}}{ED_{50}^{Hill} + dose^{Hill}} + \beta_1 \times Base$$

$$\tau = \frac{1}{Sigma^2}$$

Informative and vague priors will be included as specified in Table 4.

Details around the derivation of these priors are provided in Appendix 2.2.1. The selections of the informative priors (Prior List 1) were based on historical data and/or credible ranges for the parameters and are primarily used to aid model convergence. The vague priors (Prior List 2) are less informative and as such provide a sensitivity analysis to the informative priors.

This analysis will be conducted by the study statistician in OpenBUGS or ClinDR. QC of the analysis will be conducted by an independent statistician using the same and different starting values to test convergence of the chains, and the .txt outputs will be provided to the programming team for inclusion in the final CSR table formats.

Markov chain Monte Carlo (MCMC) methods will be used as a means of sampling from the posterior distribution of interest from the Emax model. MCMC algorithms, using Gibbs sampling, will enable calculation of the posterior distribution of the treatment differences to placebo with incorporation of the priors above.

Three chains will be run, with three diverse sets of initial values. 525,000 samples will be generated for the informative priors and 1,025,000 for vague priors and the first 25,000 will be discarded to allow for burn-in. A thin of 10 will also be originally used for the informative priors and a thin of 20 for the vague priors, resulting in 50,000 samples for summarizing the posterior nodes of interest.

If there is evidence that the chain has not converged by the end of the first 25,000 samples, the burn-in should be increased until the chains are consistent with convergence. If the MCMC error of any of the nodes of direct interest (ie, PredMeans, Diff, Prob.C1, Prob.C2) is greater than 5% of the posterior standard deviation of that node then, assuming convergence has occurred, the number of samples post burn-in may be increased so that this MCMC Error criterion is met. All other nodes monitored should be an equivalent rule, but with a 10% margin.

Model diagnostics will be examined, including trace plots, Brooks-Gelman-Rubin diagnostic plot and autocorrelation plots. If these result in concerns over model convergence, the model may be re-run with small changes such as different initial values or an increased number of samples/thinning. The final trace plots, Brooks-Gelman-Rubin diagnostic plot and autocorrelation plots will not be output for inclusion in the study report.

The posterior means, standard deviations, and 90% credible intervals (5th and 95th percentiles of the relevant posterior distribution) will be derived for each steady-state dose and for each steady-state dose contrast relative to placebo.

Statistical Model Diagnostics

The presence of outliers will be investigated for this analysis. An outlier will be defined as any response data value with a studentized (conditional) residual greater than 3, or less than -3. A listing will be presented of any participants meeting these criteria. The assumptions of normality will be verified graphically using residual plots. For each fitted model, a set of conditional studentized residual plots will be produced, including residual plot, histogram of normality, QQ plot and summary of fit statistics. The residual plots will not be included in the clinical study report.

If there are outliers or major deviations from normality then the effect of these on the conclusions will be investigated through alternative transformations and/or analyses excluding outliers. Justification for any alternative to the planned analysis will be given in the report of the study.

Example OpenBUGS code to fit this model, extract residuals and the process for this analysis is provided in Appendix 3.1.

5.2.6. Emax Model with baseline interaction

A 3-parameter dose-response Emax model with a baseline interaction will be CCI [REDACTED] and applied to the change from baseline (CFB) to Day 28 (Part A) and (as sensitivity analysis) Day 42 (Part C) CCI [REDACTED] The Emax model will include steady-state

dose as a continuous variable and baseline **CCI** as an interaction with Emax. The change from baseline will be assumed to be normally distributed with mean of 'Pred' and standard deviation of 'Sigma' as defined below:

$$CFB = \text{Normal}(Pred, Sigma)$$

Where:

$$Pred = E_0 + \left(\frac{Base}{B}\right)^{\beta_1} \times \frac{Emax \times dose}{ED_{50} + dose}$$

B is the mean overall baseline of participants included in the **CCI**. Missing values will not be imputed.

The Least Squares Means (LSMeans) together with 90% confidence intervals and standard errors will be obtained for each steady-state dose and day. Differences in LSMeans between each steady-state dose and placebo, together with 90% confidence intervals and standard errors, will also be obtained.

Standard SAS output will be provided to support the main statistical summary table for the models.

Example SAS code is provided in Appendix 3.2.

5.2.7. Analysis of Covariance (Raw Scale)

The ANCOVA model will include the change from baseline of the relevant endpoint as specified in [Section 6](#) as the dependent variable and will include treatment as a fixed effect and baseline as a covariate.

Missing values will not be imputed.

The Least Squares Means (LSMeans) together with 90% confidence intervals and standard errors will be obtained for each treatment. Differences in LSMeans between each treatment and placebo, together with 90% confidence intervals and standard errors, will also be obtained.

Standard SAS output will be provided to support the main statistical summary table for the models.

Example SAS code is provided in Appendix 3.2.

5.2.8. Analysis of Covariance (Log Scale)

The ANCOVA model will include the natural logarithmic transformed of relative change from baseline of the relevant endpoint as specified in [Section 6](#) as the dependent variable and will include treatment as a fixed effect and baseline as a covariate.

Missing values will not be imputed.

The adjusted geometric Least Squares Means (LSMeans) together with 90% confidence intervals and standard errors will be obtained for each treatment. Differences in adjusted geometric LSMeans between each treatment and placebo, together with 90% confidence intervals and standard errors, will also be obtained.

Standard SAS output will be provided to support the main statistical summary table for the models.

Example SAS code is provided in Appendix 3.2.

5.3. Methods to Manage Missing Data

For the analysis of safety endpoints, the sponsor data standard rules for imputation will be applied.

5.3.1. Pharmacokinetic Concentrations Below the Limit of Quantification

In all data presentations (except listings), concentrations below the limit of quantification (BLQ) will be set to zero. (In listings BLQ values will be reported as “<LLQ”, where LLQ will be replaced with the value for the lower limit of quantification.)

5.3.2. Deviations, Missing Concentrations and Anomalous Values

In summary tables and plots of median profiles, statistics will be calculated having set concentrations to missing if 1 of the following cases is true:

1. A concentration has been collected as ND (ie, not done) or NS (ie, no sample),
2. A deviation in sampling time is of sufficient concern or a concentration has been flagged anomalous by the pharmacokineticist/clinical team.

Note that summary statistics will not be presented at a particular time point if more than 50% of the data are missing.

6.1.1.1. Demographic and Physical Examination Data

Applicable to Parts A, B and C – Analyses reported for each part separately.

A breakdown of demographic data will be provided for age, gender, race, and ethnicity. The physical measurement (weight, body mass index and height) at baseline will also be summarized. Each will be summarized by treatment and ‘All Subjects’ in accordance with the sponsor reporting standards.

An additional table summarizing the screening data of CCI
[REDACTED] and HbA1c will be produced as above.

Finally, data collected at screening that are used for inclusion/exclusion criteria, such as laboratory data (unless noted above), duration of diabetes will be reported for randomized participants.

6.1.1.2. Discontinuation(s)

Applicable to Parts A, B and C – Analyses reported for each part separately.

Subject discontinuations, temporary discontinuations or dose reductions due to adverse events will be detailed and summarized by treatment.

Data will be reported in accordance with the sponsor reporting standards.

6.1.1.3. Adverse Events

Applicable to Parts A, B and C – Analyses reported for each part separately:

Adverse events will be reported in accordance with the sponsor reporting standards.

Incidence and severity of treatment emergent adverse event (TEAE) tables will additionally be produced (‘All causality’ and ‘Treatment related’, separately) to summarise the total number of adverse events by preferred term, which will be reported by treatment group and overall.

6.1.1.4. Hypoglycemia

Applicable to Parts A, B and C – Analyses reported for each part separately.

Any hypoglycemic AEs will be listed in a separate table and summarized categorically by treatment as per [Section 5.2.3](#).

6.1.1.5. Laboratory Data

Applicable to Parts A, B and C – Analyses reported for each part separately:

Laboratory data will be listed and summarized by treatment in accordance with the sponsor reporting standards. Baseline is as defined in [Section 3.4](#).

6.1.1.6. Vital Signs Data

Applicable to Parts A, B and C – Analyses reported for each part separately:

Absolute values and change from time-matched baseline in supine systolic and diastolic blood pressure and pulse rate will be summarized by treatment, time post-dose and day, according to sponsor reporting standards. Tables will be paged by parameter. Baseline is as defined in [Section 3.4](#).

Mean change from time-matched baseline for supine systolic and diastolic blood pressure and pulse rate will be plotted against time post-dose and day. On each plot there will be 1 line for each treatment. Data from all cohorts will be plotted on the same figure using a single line for the placebo group(s). Corresponding individual plots of change from time-matched baseline will also be produced for each treatment.

Maximum absolute values and change from time-matched baseline for vital signs will be summarized descriptively by treatment using categories as defined in [Section 5.2.3](#). Numbers and percentages of subjects meeting the categorical criteria will also be provided. All planned and unplanned post-dose timepoints will be counted in these categorical summaries. All values meeting the criteria of potential clinical concern will be listed.

The time-matched double differences in vital signs obtained following the Day 1 treatment, as defined in [Section 3.4](#), will be summarized (N, mean, 90% confidence interval) for each treatment and time point. In addition, the time-matched double differences between each treatment and placebo will be summarized (N, mean, 90% confidence interval) for each treatment, time post-dose and day.

Mean time-matched double differences in vital signs will be plotted against time post-dose for each Days as defined in the SoA separately. On each plot there will be 1 line for each treatment and a single line for the placebo group(s). Corresponding individual plots of time-matched double differences will also be produced for each treatment. The mean plots will similarly be produced for the time-matched double differences between each treatment and placebo.

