PF-07081532 PK								x ^e	x	x						x ^e	x		x ^e				x ^{e,k}	x ^k	x ^k		x			
Urine Sampling for:																									x	x		x		
Urine drug test	x	x																												
Urinalysis (and microscopy, as appropriate)	x								x	x							x							x	x		x		x	

- a. This follow-up contact may be conducted as a phone-call.
- b. Full physical exam at times indicated; limited exam for previous findings, new/open AEs, or investigator discretion.
- c. Dose administration to occur with breakfast or mixed meal daily from Day 1 to Day 28, inclusive; see Section 5.3 and Section 6.
- d. Single 12-lead ECG at Screening, follow-up and Early Termination (if applicable). Measure in triplicate at all other times indicated.
- e. Measurement/sample at 0H corresponds to the 24H timepoint as detailed in Table 2 (ie, listed in both tables, but only one sample/measurement should be collected).
- f. Single vital signs at Screening, follow-up and Early Termination (if applicable). Measure in triplicate at all other times indicated.
- g. Fingerstick glucose via glucometer on admission to CRU and prior to breakfast on all inpatient days; may be more frequent at the discretion of the investigator.
- h. Meals to be provided at approximately 0H, 4H, and 10H relative to dosing; snacks to be provided. Refer to Section 5.3.
- i. See Appendix 2 for safety lab tests to be collected at each timepoint and Section 5.3 for fasting requirements. CCl
- j. FSH in females to confirm postmenopausal status only.
- k. PK samples on Days 29, 30 and 31 to be collected 24H, 36H, 48H, and 72H after the final dose on Day 28.

Table 2. Part A (4-week in T2DM): Detailed Schedule (selected study days)

Study Day	Hours Relative to Dosing at 0H ^a													
	0	0.25	0.5	1	1.5	2	3	4	6	8	10	12	16	24 ^b
Triplet, supine 12-lead ECG	Days -1, 1, and 28, plus Day 14 or Day 21 ^k	x		x		x		x		x		x		x
Triplet, supine vital signs (blood pressure and pulse)	Days -1, 1, and 28 plus Day 14 or Day 21 ^k	x		x		x		x		x		x		x
Fasting fingerstick blood glucose measurement ^{b,c}	All inpatient days	x												
CCI														
Standardized meal/snack ^d	All inpatient days	x ^e							x		x		x	
Blinded investigational product administration	Daily: Day 1 to Day 28	x ^f												
Blood sampling for:														
- Safety laboratory tests ^g	Days -1, 14, 21, and 28	x ^h												
CCI														
- HbA1c, TSH	Days -1 and 28	x												
CCI														

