4.2.4. Endpoints

4.2.4.1. Safety

Given that the current study is the first to administer repeated doses of PF-07081532 to humans, an escalating design with careful on-going review of safety and PK of PF-07081532 is planned. Doses and dose titration schemes (if used) in the escalation sequence may be modified or repeated as guided by emerging safety, tolerability, and PK data and will be provided to investigators in writing prior to initiation of dosing.

Clinical safety laboratory tests, thorough assessments of vital signs and 12-lead ECGs, physical examinations, and AE monitoring will provide essential data to evaluate the safety and tolerability of PF-07081532. **CCI**

[figure not shown]
While GLP-1R agonists typically are not associated with hypoglycemia unless co-administered with anti-diabetic agents that can cause hypoglycemia (such as insulin or sulfonylureas), blood glucose concentrations will be monitored throughout the study via a glucometer at least once daily (pre-breakfast), and careful monitoring of symptomatic hypoglycemic AEs will be performed.

Baseline (Day -1) assessments with time-matched procedures will permit within participant comparisons, as appropriate. In addition, placebo-adjusted (between subject) comparisons of dose-response will also be conducted.

In an effort to reduce variability and better quantify any potential changes in heart rate and blood pressure (BP) during the study, all measurements of ECG and vital signs (pulse and BP) will be collected in triplicate (except as noted in the [Schedule of Activities](#)) and the mean values will be used for analysis at each time point.

[figure not shown]

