2.2. Study Design

This is a randomized, double-blind (investigator- and participant-blind), sponsor-open, placebo-controlled, multiple oral dose-escalating study of PF-07081532.

There may be 2 participant populations enrolled in this study: participants enrolling with T2DM and non-diabetic obese participants. The study will be conducted in up to 3 parts, portions of which may be conducted concurrently.

Part A: adult participants with T2DM inadequately controlled on metformin who will receive PF-07081532 or placebo daily for 28 days. Up to 5 such cohorts will be enrolled, with approximately 10 participants (8 PF-07081532: 2 placebo) per cohort. For individual participants in Part A, the duration of the study from the Screening visit to the on-site follow-up visit will be approximately 10 weeks of which approximately 33 days will be inpatient at the CRU.

Part B (optional): obese (non diabetic) adult participants who will receive PF-07081532 or placebo daily for 42 days. This is an optional study part for which up to 2 cohorts may be enrolled with approximately 15 obese participants (12 PF-07081532: 3 placebo) per cohort.

[figure not shown]
CCI

For individual participants in Part B, the duration of the study from the Screening visit to the on-site follow-up visit will be approximately 12 weeks of which approximately 48 days will be inpatient at the CRU.

Part C (optional): adult participants with T2DM inadequately controlled on metformin who will receive PF-07081532 or placebo daily for 42 days. Up to 2 cohorts of 10 participants (8 PF-07081532: 2 placebo per cohort) may be enrolled if judged necessary to meet the study objectives. For individual participants in Part C, the duration of the study from the Screening visit to the on-site follow-up visit will be approximately 12 weeks of which approximately 47 days will be inpatient at the CRU.

In all study parts, participants will initially return to the clinical research unit (CRU) 7 to 14 days after the last administration of IP for an on-site follow-up visit. A further follow-up contact with participants will be conducted at least 28 days and up to 35 days after the last administration of IP; this contact may be done via a phone call.

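### Blood pressure and pulse are compared with placebo only one time point at a time; adding a serial-day mean would estimate a sustained shift with a narrower interval from the same readings.

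*SAP*

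**What the plan says.** Vital signs are part of the primary safety endpoint. Protocol Table 2 (Part A) schedules serial triplicate ECGs and vital signs on "Days -1, 1, and 28, plus Day 14 or Day 21", with seven marks in the vital-signs row. Protocol 4.2.4.1 explains the triplicates: "In an effort to reduce variability and better quantify any potential changes in heart rate and blood pressure (BP) during the study". The same sentence goes on to say that the triplicate mean is what is analysed at each time point.

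SAP 6.1.1.6 says that values and time-matched changes in "supine systolic and diastolic blood pressure and pulse rate will be summarized by treatment, time post-dose and day, according to sponsor reporting standards". Confidence intervals are attached to the double difference defined in SAP 3.1.3. After Day 1 dosing it "will be summarized (N, mean, 90% confidence interval) for each treatment and time point". For the placebo comparison, "the time-matched double differences between each treatment and placebo will be summarized (N, mean, 90% confidence interval) for each treatment, time post-dose and day". SAP 6.1.1.7 does the same for ECG heart rate.

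The summaries that span times are maxima and categories: maximum values and changes for vital signs, and maximum heart-rate increase by period and overall. The legible text of either section gives no mean over the times of a day.

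**The concern.** A once-daily drug may move pulse or blood pressure for much of the day. If so, the readings on a serial day all inform one quantity, the average shift, and no single nominal time uses them all. The plan leaves the reader to judge a sustained effect from a large set of wide intervals, or from maxima. A maximum over several noisy readings tends to lie above the mean effect and comes with no interval for it. What is at stake is how clearly the study report can state a modest sustained heart-rate or blood-pressure effect, or its absence, from data already being collected.

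**Working it through.** The documents give no SD, correlation, power or precision figure for vital signs, so there is no plan figure to reproduce.

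**Inputs from the documents.** SAP 2.2: "Up to 5 such cohorts will be enrolled, with approximately 10 participants (8 PF-07081532: 2 placebo) per cohort", so at most 40 active and 10 placebo participants in Part A. There are three parameters (systolic, diastolic, pulse) and three serial dosing days (1, 14 or 21, and 28). The seven marks are read as 0H plus six later times; the table is broken, so the exact hours are unclear. Each cohort is taken as one treatment. Pooling of placebo is read from the single placebo line on the SAP figures.

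**1. Number of placebo contrasts.** 5 × 3 × 3 × 6 = 270, or × 7 = 315. With six times on Day 1 (0H is zero by construction) and seven on the other days, 5 × 3 × (6 + 7 + 7) = 300. The Day 1 within-treatment intervals add about 6 groups × 3 × 6 = 108. A serial-day mean needs 5 × 3 × 3 = 45.

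**2. Width of one interval.** Half-width = t(0.95, df) × SD × √(1/n₁ + 1/n₂).
- 8 active v 10 pooled placebo, df 16: 0.83 SD.
- 8 v 2 within one cohort, df 8: 1.47 SD.

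**3. Averaging time-matched changes.** The SE of a k-time mean relative to one time is √((1 + (k − 1)r)/k), where r is the within-day correlation of the changes (assumed). For k = 6:

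| r | SE ratio | Narrower by |
|---|---|---|
| 0.3 | 0.645 | 35% |
| 0.5 | 0.764 | 24% |
| 0.7 | 0.866 | 13% |
| 0.8 | 0.913 | 9% |

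The half-width of 0.83 SD falls to 0.53 SD (r = 0.3) or 0.76 SD (r = 0.8). Using five times changes little: √(2.2/5) = 0.663 (34% narrower) at r = 0.3 and √(4.2/5) = 0.917 (8%) at r = 0.8.

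**4. Averaging the SAP's double difference.** All times share the Day 1 and Day −1 0H readings, which raises their correlation. With residual variance σ² and day-effect variance τ², r = 0.5 on Day 1 if residuals are independent, so the gain is 24%. On later days r = (σ² + τ²)/(2σ² + τ²), which is at least 0.5. With σ² = 1, the Day 28 gain is 24% at τ² = 0, and 19%, 15% and 11% at τ² = 0.43, 1 and 2. A simulation with 400,000 draws agreed. Positive serial correlation of the residuals lowered the gain further.

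**5. Mean change against the planned interval.** The planned intervals belong to the double difference, so steps 3 and 4 each compare like with like but do not cross over. In the same model (σ² = 1), a six-time mean change has variance 2τ² + 2/6. A single-time double difference has variance 4 + 2τ² on later days, so the mean change is always the tighter there. On Day 1 day effects cancel and its variance is 4. The mean change is then tighter only while 2τ² + 1/3 < 4, that is τ² < 1.83, or a change correlation τ²/(1 + τ²) below about 0.65.

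**The case against.** The strongest reply is that nothing here departs from the protocol. A reader might infer from the stated aim of reducing variability that the SAP fails the protocol's purpose. It does not: the tool named in that sentence is triplicate averaging, the analysis is to be made at each time point, and the SAP follows this. That stands.

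A reader might also count one interval in ten excluding zero by chance, 27 to 32 of them, and call it a type I error problem. The documents do not support that. Protocol 9.1 has no hypothesis tests and SAP 6.1.1 plans no formal safety analysis. The intervals are also correlated. The number is a matter of readability.

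Nor do these intervals drive escalation. The vital-sign criterion in Protocol 6.6.1 counts participants with clinically significant abnormalities, and escalation reviews take place before all five cohorts have supplied their placebo participants.

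Two further points stand. Mean and individual profiles already show informally whether an effect lasts. SAP Appendix 3.2.5 holds a safety ANCOVA whose label is partly redacted, so an averaged endpoint there cannot be excluded; the claim is limited to legible text.

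Finally, this is the first repeated-dose study in humans, and short-lived peaks matter. That is a good reason not to rank a day mean above the per-time results. It is not a reason to leave the mean out, because maxima and profiles give no interval for an average shift.

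**Conclusion.** The point holds as a low-cost improvement, not as an error. In Part A the plan gives about 270 to 315 placebo-adjusted intervals for blood pressure and pulse, each about ±0.83 SD if placebo is pooled, and no legible estimate of a mean effect over the day.

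The gain is a range. A serial-day mean of time-matched changes has an interval about 9% to 35% narrower than a single-time change, for an assumed within-day correlation of 0.8 to 0.3. A reader might take one end of that range as the expected gain, but neither document gives the correlation. If the double difference is averaged, the gain is at most about 24% under the models tried, and about 11% to 20% on later days with moderate day effects. These figures assume equal variances across times and an effect that lasts over the averaged hours.

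**What to change.** In SAP 6.1.1.6, and for heart rate in 6.1.1.7, add one derived variable: for each participant and serial day, the mean of the time-matched changes over a prespecified set of post-dose nominal times. Use the same times on Day −1 and on the dosing day. State whether 24H is included, since Table 2 has that reading taken before the next morning's dose. State too that the averaged quantity is the time-matched change and not the double difference, because on Day 1 the choice affects how day effects enter.

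Report the treatment-minus-pooled-placebo difference with a 90% interval by treatment and day, which is 45 contrasts for blood pressure and pulse in Part A. Present it alongside the per-time tables, plots and maxima, neither replacing them nor ranked above them.

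The cost is one derivation and one extra table per parameter, with no new data. The downside is that a day mean can blunt a short-lived peak, which the retained per-time results still show.
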